5.1.2 Treatment monitoring and dose modifying strategies

The following AEs, laboratory assessment results or changes in concurrent medications require evaluation and discussion with the GSK medical monitor within 24 hours of the investigator becoming aware of the event.

Dose Adjustment and Discontinuation

If a subject experiences a clinically significant AE and this AE continues at the next scheduled dose, or could potentially be exacerbated by the next dose, the investigator may delay the next dose by up to 2 weeks or withhold 1 dose, per physician discretion. As a result, any subsequent study visits will be adjusted. If a similar concern is present at the time of the next scheduled dose, any decision made to discontinue treatment will be driven by the Investigator's clinical judgment. Laboratory tests will be repeated per Investigator's discretion.

If it is determined that investigational product should be discontinued, the subject should be followed at regularly scheduled monthly study visits as required until resolution of the AE, and return for follow-up visits as described in Subject Withdrawal Criteria.

For a full listing of the discontinuation criteria, please see section 3.5 of the protocol.

Hypogammaglobulinemia

Benlysta should be discontinued in subjects with IgG levels <250 mg/dL associated with a severe or serious infection. For IgG concentrations < 250 mg/dL that are not associated with a severe or serious infection, increased vigilance for infection is required. Clinical judgment should be applied with respect to the appropriateness of continuing study therapy in these subjects. If a subject experiences any IgG levels < 250 mg/dL, the dose of study agent must be withheld and the Medical Monitor and GlaxoSmithKlein must be consulted before administering any subsequent dose of study agent. If a subject experiences a clinically significant, potentially life-threatening (Grade 4) AE that the investigator believes may be definitely, possibly or probably related to study agent, then treatment with study agent will be discontinued. The subject should be withdrawn from study agent, and followed at regularly scheduled study visits as specified by protocol and also until resolution of the AE(s) (whichever is longer).

Liver Chemistry Stopping Criteria

Liver chemistry threshold stopping criteria have been designed to assure subject safety and to evaluate liver event etiology (in alignment with the US Food and Drug Administration premarketing clinical liver safety guidance).

Study treatment will be stopped if any of the following liver chemistry stopping criteria is met:

1. Alanine aminotransferase (ALT) \square 3x upper limit of normal (ULN) and total bilirubin \square 2xULN (>35% direct bilirubin); or ALT \square 3xULN and international normalized ratio

(INR) \geq 1.5. NOTE: serum bilirubin fractionation should be performed if testing is available. If fractionation is unavailable, urinary bilirubin is to be measured via dipstick (a measurement of direct bilirubin, which would suggest liver injury).

2. ALT \geq 5xULN.
3. ALT \geq 3xULN if associated with symptoms (new or worsening) believed to be related to hepatitis (such as fatigue, nausea, vomiting, right upper quadrant pain or tenderness or jaundice) or believed to be related to hypersensitivity (such as fever, rash or eosinophilia).
4. ALT \geq 3xULN persists for \geq 4 weeks.
5. ALT \geq 3xULN and cannot be monitored weekly for 4 weeks.
6. ALT \geq 5xULN but $<$ 8xULN and labs cannot be monitored weekly for \geq 2 weeks

Subjects with ALT \geq 3xULN and $<$ 5xULN and bilirubin $<$ 2xULN, who do not exhibit hepatitis symptoms or rash, can continue study treatment as long as they can be monitored weekly for 4 weeks.

Concurrent Medication- Prohibited

Subjects who receive concurrent medication or treatment that is prohibited for safety reasons (e.g. live vaccines, cyclophosphamide or B-cell agents such as rituximab) should be withdrawn from study treatment and should not receive additional investigational product without the explicit approval of the Medical Monitor (Funding Sponsor).

Required Actions, Monitoring, and Follow up Assessments following ANY Liver Stopping Event

Actions:

- Immediately discontinue study treatment
- Report the event to GSK within 24 hours
- Complete the liver event CRF and complete SAE data collection tool if the event also meets the criteria for an SAE (All events of ALT \geq 3xULN and bilirubin \geq 2xULN ($>35\%$ direct bilirubin) or ALT \geq 3xULN and INR >1.5 , if INR measured which may indicate severe liver injury (possible 'Hys Law'), must be reported as an SAE (excluding studies of hepatic impairment or cirrhosis); INR measurement is not required and the threshold value stated will not apply to subjects receiving anticoagulants)
- Perform liver event follow up assessments
- Monitor the subject until liver chemistries resolve, stabilize, or return to within baseline (see MONITORING below)
- Do not restart/rechallenge subject with study treatment unless allowed per protocol and GSK Medical Governance approval is granted **Monitoring:**

For bilirubin or INR criteria:

- Repeat liver chemistries (include ALT, AST, alkaline phosphatase, bilirubin) and perform liver event follow up assessments within **24 hrs**

- Monitor subjects twice weekly until liver chemistries resolve, stabilize or return to within baseline
- A specialist or hepatology consultation is recommended For All other criteria:
- Repeat liver chemistries (include ALT, AST, alkaline phosphatase, bilirubin) and perform liver event follow up assessments within 24-72 hrs
- Monitor subjects weekly until liver chemistries resolve, stabilize or return to within baseline

Follow Up Assessments:

- Viral hepatitis serology (Includes: Hepatitis A IgM antibody; Hepatitis B surface antigen and Hepatitis B Core Antibody (IgM); Hepatitis C RNA; Cytomegalovirus IgM antibody; Epstein-Barr viral capsid antigen IgM antibody (or if unavailable, obtain heterophile antibody or monospot testing); Hepatitis E IgM antibody) Serum creatine phosphokinase (CPK) and lactate dehydrogenase (LDH).
- Fractionate bilirubin, if total bilirubin \geq 2xULN
- Obtain complete blood count with differential to assess eosinophilia
- Record the appearance or worsening of clinical symptoms of liver injury, or hypersensitivity, on the AE report form
- Record use of concomitant medications on the concomitant medications report form including acetaminophen, herbal remedies, other over the counter medications
- Record alcohol use on the liver event case report form For bilirubin or INR criteria:
- Anti-nuclear antibody, anti-smooth muscle antibody, Type 1 anti-liver kidney microsomal antibodies, and quantitative total immunoglobulin G (IgG or gamma globulins).
- Serum acetaminophen adduct HPLC assay (quantifies potential acetaminophen contribution to liver injury in subjects with definite or likely acetaminophen use in the preceding week [James, 2009]). NOTE: not required in China
- Liver imaging (ultrasound, magnetic resonance, or computerised tomography) and /or liver biopsy to evaluate liver disease: complete Liver event case report form

Increased Monitoring Criteria with Continued Therapy

Criteria

- If ALT \geq 5xULN and $<$ 8xULN and bilirubin $<$ 2xULN without symptoms believed to be related to liver injury or hypersensitivity, and who can be monitored weekly for 2 weeks **OR**
- ALT \geq 3xULN and $<$ 5xULN and bilirubin $<$ 2xULN without symptoms believed to be related to liver injury or hypersensitivity, and who can be monitored weekly for 4 weeks

Required Actions

- Notify the GSK medical monitor within 24 hours of learning of the abnormality to discuss subject safety.
- Subject can continue study treatment
- Subject must return weekly for repeat liver chemistries (ALT, AST, alkaline phosphatase, bilirubin) until they resolve, stabilize or return to within baseline

- If at any time subject meets the liver chemistry stopping criteria, proceed as described above for Required Actions and Follow up Assessments following ANY Liver Stopping Event
- If ALT decreases from ALT ≥ 5 xULN and < 8 xULN to ≥ 3 xULN but < 5 xULN, continue to monitor liver chemistries weekly.
- If, after 4 weeks of monitoring, ALT < 3 xULN and bilirubin < 2 xULN, monitor subjects twice monthly until liver chemistries normalize or return to within baseline.

5.1.3 Duration of Treatment and Follow-up.

The above treatment protocol is investigational. However all patients will be treated and monitored according to our standard of care for kidney transplant patients. DSA will be monitored pre-transplant and at 1, 3, 6, 9, and 12 months. We will perform a protocol biopsy at 1 year post-transplant per standard of care.

Data for the study will be collected for 1 year post transplant via REDCap. We will collect medical health information generated as part of post-transplant standard of care clinic visits, lab analysis and procedures done within the year. If the kidney fails and patient returns to dialysis the study coordinator or the PI will contact the patient's dialysis unit and local nephrologists every three months for one year post transplant to collect the necessary safety monitoring information including infectious (such as herpes simplex virus) and hematological complications, and lab results.

6. Study Procedures

The following assessments will be obtained for all subjects, as outlined in the Study Visit Schedule of Events (Appendix A).

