3.6 Criteria for Terminating the Study

The Principal Investigator will review safety and efficacy criteria on an ongoing basis. The study enrollment will be halted and data reviewed by the Data Safety Monitoring Committee and the University of Wisconsin Health Sciences Institutional Review Board for any of the following:

- 1) If greater than two patients are discontinued from study treatment due to elevated liver function tests as described in the protocol.
- 2) If greater than two patients develop hypogammaglobulinemia and infectious complications resulting in discontinuation of study treatment
- 3) Death of one or more patients.

After this review, the Investigator, Data Safety Monitoring Committee and the IRB will jointly make a final determination regarding continuation, modification, or termination of the study. The study can be terminated at any time for any reason by the Principle Investigator or GlaxoSmithKline, Inc. Should this be necessary, the patient should be seen as soon as possible. The investigator may be informed of additional procedures to be followed in order to ensure that adequate consideration is given to the protection of the patient's interests. The investigator will be responsible for informing the DMC, IRB and the FDA of the early termination of the trial.

See Section 7.3 for information on the ICTR Data Monitoring Committee (DMC) for this study.

4. Selection of Subjects

Potential subjects will be identified prior to kidney transplant based on the following inclusion and exclusion criteria.

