- Currently on any suppressive therapy for a chronic infection (such as tuberculosis, pneumocystis, cytomegalovirus, herpes simplex virus, herpes zoster and atypical mycobacteria).
- Hospitalization for treatment of infection within 60 days of Day 0
- Use of parenteral (IV or IM) antibiotics (antibacterials, antivirals, anti-fungals, or anti parasitic agents) within 60 days of Day 0
- Have a history of a primary immunodeficiency
- Uncontrolled infection or any other unstable medical condition that could interfere with the study
- Seropositive for HIV, HCV or HBV, except for hepatitis B surface antibody positive If the HIV, HCV or HBV screening virology results are not available prior to transplantation then the most recent historical result (within the last 6 months) will be used.
- Have a significant IgG deficiency (IgG level < 400 mg/dl) Have an IgA deficiency (IgA level < 10 mg/dL)
- Prior therapy at any time: has ever received any of the following: a) B-cell targeted therapy (e.g., rituximab, other anti-CD20 agents, anti-CD2 [epratuzumab], antiCD52 [alemtuzumab], BLyS-receptor fusion protein [BR3], TACI fragment, crystallizable (Fc), belimumab), or IV cyclophosphamide
- Live vaccines within 30 days
- Have a history of an anaphylactic reaction to parenteral administration of contrast agents, human or murine proteins or monoclonal antibodies
- Patients with a lymphocyte count <500/mm³
- Patients with evidence of current drug or alcohol abuse or dependence.
- Patients with venous access limitations likely to preclude monthly infusions
- Patients whom are unlikely to comply with scheduled study visits based on investigator judgment or has a history of substance abuse, psychiatric disorder or condition that may compromise communication with the investigator
- Myocardial infarction within 6 months prior to enrollment or New York Heart Association (NYHA) Class III or IV heart failure, uncontrolled angina, severe uncontrolled ventricular arrhythmias, or electrocardiography evidence of acute ischemia or active conduction system abnormalities
- Diagnosis of liver cirrhosis or chronic viral hepatitis

- Female subject is pregnant or breast-feeding. Confirmation that the subject is not pregnant must be established by a negative serum β -human chorionic gonadotropin (β -hCG) pregnancy test result obtained during screening. Pregnancy testing is not required for post-menopausal or surgically sterilized women

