6.2 Day of Transplant (Day 0)

The first dose of investigational product will be administered on Day 0 intra-operatively. The dose of investigational product administered may not be altered. The rate of infusion may be slowed or interrupted if the subject appears to develop signs of adverse reactions or infusion-related symptoms. At later visits, these subjects may continue to be infused over a longer infusion period at the investigator's clinical discretion. The rate of infusion should not be increased above the recommended rate.

Blood pressure and heart rate will be recorded within 15 minutes prior to belimumab infusion, at 15 ± 5 minutes after the beginning of the infusion, and 15 ± 5 minutes following completion of the infusion.

Biopsy will be obtained at transplant per standard of care.

6.3 Post-Transplant Study Visits: Week 1, Week 2, Month 1, 2, 3, 4, 5, 6, 9, 12

Study visits will occur at Week 1 +/- 3 days (while in the hospital recovering from surgery), Week 2, and Months 1, 2, 3, 4, 5, 6, 9, and 12, after transplant in conjunction with standard of care. With the exception of the Week 2 visit that will take 3 hours, visits that include a belimumab infusion (Months 1, 2, 3, 4, 5) will take about 2 hours to complete. The remainder of study visits will only take about an hour. Many of the procedures required for the study are the same as those done at standard of care clinic visits and will not require additional procedures/tests. At these visits, the following procedures and tests will occur:

- Collection of vital signs (including temperature, blood pressure, heart and breathing rate, and weight), at all visits
- A brief physical exam
- Blood and urine sample collections for standard laboratory tests (all visits), except when the study subject is anuric or oliguric, and/or unable to provide a urine sample.
- Review of medications (on day of study visit.)
- Research blood sample collection at Months 1, 3, 6, 9, 12 (if consented)
- Any changes to health or medical history will be recorded and assessed

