6.3.1 Study Treatment

- Belimumab: 10 mg/kg/dose will be administered IV for 6 months at the following intervals: at time of transplant (Day 0), then post -transplant at Weeks 2, 4, 8, 12, 16, and 20.

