6.3.3 Laboratory Assessments

Laboratory assessments will be performed according to the schedule of events in Appendix A.

Post-transplant follow-up standard of care labs results will be collected via the Transplant Data System every month for the first year post-transplant for safety monitoring.

Subjects who do not receive a transplant, following belimumab injection, will have their labs and clinical care monitored quarterly by the study coordinators, or the PI who will collect the data from UWHC electronic records or request records from the subject's provider if not within the UWHC system.

Subjects will also have a kidney biopsy at 1 year post-transplant per standard of care.

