11.0 Appendix A (Schedule of Events)

	CAMPBEL Trial												
	Screen	Hospitalization	Outpatient Visit										
			Day of Transplant (Day 0)	1 Week	2 Weeks	4 Weeks Month 1	8 Weeks	Weeks Month 3	Weeks	Weeks	Weeks Month 6	Weeks Month 9	Weeks Month 12
	≤30 days prior to transplant	May be same day as screening		□ 3d	□ 3d	□ 3d	□ 3d	□ 3d	□ 3d	□ 3d	□ 7d	□ 7d	□ 7d
Informed Consent	X												
Demographics	X												
Medical History	X												
Physical Exam	X			X	X	X	X	X	R	R	X	X	X
Vital Signs (+ weight) ¹	X	XΔ		X	X	X	X	X	R	R	X	X	X
Hematology ^{2*}	X	X		X	X	X	X	X	R	R	X	X	X
Comprehensive Metabolic Panel*	X	X		X	X	X	X	X	R	R	X	X	X
Urine Protein/ Creatinine*	X	X		X	X	X	X	X	R	R	X	X	X
Serum pregnancy test ^{3**}	X	X			R ⁸	R ⁸	R ⁸	R ⁸	R ⁸	R ⁸			
PRA*	X	X				X		X			X	X	X
Anti HLA antibodies by Luminex*	X	X				X		X			X	X	X
ECG*	X												
Viral Serology ^{3*}	X	X											
Immunoglobulin Panel: IgG, IgA, IgM by clinical lab*	X					X	X	X	X	X	X	X	X
Tacrolimus Trough				X	X	X	X	X	X	X	X	X	X
Steroid Taper		X											
Alemtuzumab		X											
Tacrolimus/ Mycophenolic Acid ⁹		X	X	X	X	X	X	X	X	X	X	X	X
Belimumab ⁴		R ⁴		R ⁴	R ⁴	R ⁴	R ⁴	R ⁴	R ⁴	R ⁴			
Kidney biopsy ⁵		X											X
Adverse Events ⁶		R ⁶	R ⁶	R ⁶	R ⁶	R ⁶	R ⁶	R ⁶	R ⁶	R ⁶	R ⁶	R ⁶	R ⁶
Con Meds	R		R	R	R	R	R	R	R	R	R	R	R
Cytokine Analysis ⁷	R	R			R		R			R	R	R	R
T Lymphocyte Analysis ⁷	R	R			R		R			R	R	R	R
B Lymphocyte Analysis ⁷	R	R			R		R			R	R	R	R
Immunoglobulin Analysis (IgM, IgA, IgG) ⁷	R	R			R		R			R	R	R	R
BAFF/APRIL Analysis ⁷	R	R			R		R			R	R	R	R

¹ Vital signs include temperature, blood pressure, pulse and respiratory rate recorded prior to each study drug dose.

² Hematology: CBC and differential

³ HIV, HBsAg, anti-HBc, anti-HBs antibodies, hepatitis C antibody, herpes simplex virus, CMV, Epstein Barr virus, and varicella zoster virus per standard of care. For eligibility assessment, if the screening virology results for HIV, HCV and HBV are not available prior to transplantation then the most recent historical result (within the last 6 months) will be used. Per standard of care, the viral serology tests for CMV, Epstein Barr Virus, and varicella are not to be repeated once found positive.

⁴ Belimumab infusion ⁵ Kidney biopsy will be performed at time of transplant per standard of care, and at 1 year to assess histologic response per standard of care.

⁶ Adverse events recorded prior to each study drug dose and will include subject reports of changes in sleep patterns, anxiety and suicidality

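### Belimumab must be held at any IgG below 250 mg/dL, but no clinical IgG is scheduled between screening and Week 4: the Week 2 dose has no post-transplant value behind it, and the Week 4 dose only a same-visit draw

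*Combined protocol and SAP*

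**What the plan says.** Section 5.1.2 (Hypogammaglobulinemia) states: "If a subject experiences any IgG levels < 250 mg/dL, the dose of study agent must be withheld". The medical monitor and the funder must then be consulted before any further dose. The same paragraph leaves continuation to clinical judgment when IgG is below 250 mg/dL without a severe or serious infection, but the withholding sentence covers any value below the cut-off.

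Section 6.3.1 gives belimumab on the day of transplant, "then post -transplant at Weeks 2, 4, 8, 12, 16, and 20". Section 6.3.3 states: "Laboratory assessments will be performed according to the schedule of events in Appendix A". In Appendix A the row "Immunoglobulin Panel: IgG, IgA, IgM by clinical lab" is marked at screening, at Weeks 4, 8, 12, 16 and 20, and at Months 6, 9 and 12. It is blank at Day 0, Week 1 and Week 2.

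The exclusion criteria (Section 4.2) rule out subjects who "Have a significant IgG deficiency (IgG level < 400 mg/dl". In the dose-adjustment paragraph of Section 5.1.2, unscheduled testing is left open: "Laboratory tests will be repeated per Investigator's discretion".

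**The concern.** The hold applies whether or not the subject has symptoms, so only an IgG measurement can trigger it. Examination, blood count and adverse event review at Weeks 1 and 2 may lead the investigator to hold a dose for other reasons, but none of them measures IgG. A symptom-free subject whose IgG had fallen below 250 mg/dL could therefore receive the Week 2 dose although the protocol requires it to be withheld. The low value would come to light before that dose only if the investigator chose to order a test.

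By Week 2 the subject has had alemtuzumab, high-dose steroid and one belimumab infusion, and has started tacrolimus and mycophenolic acid. Section 1.3 states that there is no experience of belimumab combined with alemtuzumab or tacrolimus, so these documents give no basis for ruling out an early fall. What is at stake is one safety check, not the reading of the results.

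**Working it through.** The plan states no figure on this point. The check maps visits to doses and adds simple arithmetic.

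**1. Reading the table.** Each Appendix A row has 13 cells after its label: screening, two Day 0 cells, Weeks 1, 2, 4, 8, 12, 16 and 20, and Months 6, 9 and 12. The clinical immunoglobulin row has one mark at screening and eight consecutive marks ending at Month 12. There are ten post-transplant visits, so 10 − 8 = 2 are blank: Weeks 1 and 2. Three other rows read on the same columns agree with the text or the column headings:
- Physical exam: all ten post-transplant visits.
- PRA: Weeks 4 and 12, then Months 6, 9 and 12.
- Pregnancy test: Weeks 2, 4, 8, 12, 16 and 20, which are the six post-transplant doses named by footnote 8.

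Two sets of marks do not agree with the text. The belimumab row shows eight marks against seven doses, with the extra one at Week 1. The research sample rows fall at Weeks 2, 8 and 20 where the text has Months 1 and 3. Neither is used here for timing.

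**2. Scheduled post-transplant clinical IgG behind each dose.**

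| Dose visit | At or before the visit | Strictly before the visit |
|---|---|---|
| Week 2 | none | none |
| Week 4 | Week 4 | none |
| Week 8 | Weeks 4, 8 | Week 4 |
| Week 12 | Weeks 4, 8, 12 | Weeks 4, 8 |
| Week 16 | Weeks 4 to 16 | Weeks 4 to 12 |
| Week 20 | Weeks 4 to 20 | Weeks 4 to 16 |

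Planned post-transplant infusions: 5 subjects × 6 = 30.
- Counting same-visit draws, Week 2 alone lacks a value: 5/30 = 16.7%.
- Counting only earlier draws, Weeks 2 and 4 both lack one: 10/30 = 33.3%.

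**3. Other possible sources.** Section 7 names hematology and hepatic tests before each cycle, but not IgG. The research immunoglobulin sample in Section 6.3.5 is optional. The text places it before transplant and at Months 1, 3, 6, 9 and 12, and says that results from banked samples do not guide care.

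**4. Age of the screening value at the Week 2 dose.** Screening is 0 to 30 days before transplant. The Week 2 window is read as ±3 days, as Section 6.3 states for Week 1 ("Study visits will occur at Week 1 +/- 3 days (while in the hospital recovering from surgery").
- Youngest: 0 + 14 − 3 = 11 days.
- Oldest: 30 + 14 + 3 = 47 days.

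**5. Fall needed to reach 250 mg/dL**, as (baseline − 250)/baseline:
- 400 (the entry floor): 150/400 = 37.5%.
- 500: 250/500 = 50%.
- 700: 450/700 = 64.3%.
- 1000: 750/1000 = 75%.

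The baselines of 500 to 1000 are assumptions; the documents give no baseline IgG.

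**6. Effect of a Week 1 draw** (Day 4 to 10).
- At the Week 2 dose (Day 11 to 17) it is 11 − 10 = 1 to 17 − 4 = 13 days old.
- At the Week 4 dose (Day 25 to 31) it is 25 − 10 = 15 to 31 − 4 = 27 days old.
- All six post-transplant doses would then have a post-transplant value from before the dose visit.

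**The case against.** The strongest reply is that no rule is broken. Section 5.1.2 is reactive: it says what to do once the investigator learns of a low value, and it does not require an IgG result before each dose. Where the protocol wants a test before dosing it says so, as it does for pregnancy, hematology and hepatic function. This stands. A reader might infer that Section 5.1.2 and Appendix A contradict each other, and they do not. The schedule simply leaves a mandatory hold with no scheduled test that could trigger it at Week 2.

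No risk is quantified either. A fall of 37.5% or more within about two weeks of transplant is large, and the documents give no likelihood for it. This also stands. The 16.7% counts infusions and does not estimate undetected hypogammaglobulinemia.

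A reader might take Week 2 to be the only dose affected. That depends on crediting Week 4 with a draw at the dosing visit, and nothing requires that result to be known before the infusion.

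A reader might also tie the gap to the enrollment-halting criterion in Section 3.6, "If greater than two patients develop hypogammaglobulinemia and infectious complications resulting in discontinuation of study treatment". The documents do not support that. The criterion needs more than two of five subjects to stop treatment with infectious complications as well, and a missing Week 2 IgG does not alter it.

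Lastly, the evidence is one row of a table in which other rows are misaligned. Section 6.1 does not list IgG even among the screening tests, so no body text confirms the row. Its agreement with three other rows supports the reading, but only with medium confidence.

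**Conclusion.** The point holds as a minor safety-schedule gap. No clinical IgG is scheduled between screening and Week 4, so the Week 2 dose has no post-transplant value at or before its visit, and the Week 4 dose has only a same-visit draw. The screening value cannot trigger the hold, since entry requires at least 400 mg/dL.

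The gap covers one dose per subject in five subjects, or two if only earlier draws count. The withholding rule is not wrong, and discretionary testing remains available. No endpoint, analysis or halting criterion changes. The conclusion rests on the Appendix A row being aligned as read above and on the visit windows being ±3 days. It does not claim that an early fall is likely.

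**What to change.** In Appendix A, mark the row "Immunoglobulin Panel: IgG, IgA, IgM by clinical lab" at Week 1 as a research procedure (R), on the blood already drawn at that visit for hematology. Add this footnote: *The Week 1 IgG result is reviewed before the Week 2 belimumab infusion.* The same draw gives the Week 4 dose an earlier post-transplant value.

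Cost: one extra assay per subject, about five in all, and one table mark with its footnote. The amendment needs IRB approval before use (Section 8.1), and Section 8.2 ties a consent form update to any amendment. The Week 1 draw comes nominally 7 days before the Week 2 infusion (range 1 to 13), so a short wait for the result would be only occasional.

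### Asymptomatic, monitorable subjects with ALT from 5 to below 8 times ULN are told both to stop and to continue belimumab, and the study-halt count depends on which instruction is followed

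*Combined protocol and SAP*

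**What the plan says.** Section 5.1.2, Liver Chemistry Stopping Criteria, opens with "Study treatment will be stopped if any of the following liver chemistry stopping criteria is met" and lists six items. Item 2 is ALT ≥5xULN, with no upper limit and no bilirubin, symptom or monitoring condition. Item 6 reads "ALT \geq 5xULN but $<$ 8xULN and labs cannot be monitored weekly for \geq 2 weeks". The one continuation sentence in that part covers ALT ≥3x and <5xULN with bilirubin <2xULN: such subjects, "who do not exhibit hepatitis symptoms or rash, can continue study treatment as long as they can be monitored weekly for 4 weeks". After any liver stopping event the first required action is "Immediately discontinue study treatment".

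Still in Section 5.1.2, Increased Monitoring Criteria with Continued Therapy lists two groups. The first is ALT ≥5x and <8xULN with bilirubin <2xULN, "without symptoms believed to be related to liver injury or hypersensitivity, and who can be monitored weekly for 2 weeks". The second is the 3 to <5xULN band with 4 weeks of weekly monitoring. For both groups the required actions include "Subject can continue study treatment". A later bullet sends anyone who meets a stopping criterion at any time back to the stopping actions. Another gives instructions for ALT falling from the 5 to <8x band into the 3 to <5x band.

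Section 3.6, criterion 1, halts enrollment for committee and IRB review: "If greater than two patients are discontinued from study treatment due to elevated liver function tests as described in the protocol".

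**The concern.** One laboratory result in one subject leads to two different mandated courses. Stopping brings immediate discontinuation, a liver event form, a work-up for cause, and no rechallenge unless the protocol allows it and the drug company's medical governance approves. Continuing means further infusions with weekly liver tests. Section 1.3 says there is no experience of belimumab combined with alemtuzumab or tacrolimus, so this is a rule that staff should not have to interpret.

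There is also a consequence at study level. Section 3.6 counts discontinuations for liver tests by reference to the protocol. If the protocol gives two answers for a band of ALT values, the count that triggers the halt has two possible values for the same data.

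**Working it through.** The plan states no figure for this point, so there is none to reproduce. The check sets the two rules side by side and then looks at the halt count.

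**1. Rules applied to one profile.** Take bilirubin <2xULN, INR <1.5, no symptoms, weekly monitoring possible and no 4-week persistence. Items 1, 3, 4, 5 and 6 then do not apply, which leaves item 2 and the increased-monitoring criteria.

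| ALT (xULN) | Stopping item met | Increased monitoring allows continuation | Result |
|---|---|---|---|
| 2.9 | none | not applicable | no rule triggered |
| 3.0, 4.9 | none | yes | continue |
| 5.0, 6.5, 7.9 | item 2 | yes | **stop and continue** |
| 8, 10 | item 2 | no | stop |

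The direct conflict is ALT ≥5x and <8xULN, with the upper limit excluded. It needs the bilirubin, symptom and monitoring conditions. Where those fail, the increased-monitoring criterion gives no permission and item 2 stops treatment unopposed.

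**2. Item 6 against item 2.** Item 6 requires ALT ≥5x and <8xULN and no weekly monitoring. Every such subject already has ALT ≥5xULN and so meets item 2. Across all combinations of ALT level, bilirubin, INR, symptoms, monitoring and persistence examined, item 6 never applied without item 2. As written it has no effect. It makes sense only if some subjects in that band may continue.

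**3. The return clause.** For items such as new symptoms or 4-week persistence, sending a subject back to the stopping actions works as intended, because those can arise after increased monitoring begins. For item 2 it cannot work that way. A subject who enters under the first increased-monitoring criterion has ALT ≥5xULN by definition, so the permission is withdrawn as soon as it is given.

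**4. Other places that might settle it.** Section 5.1.2 refers to Section 3.5 for the full list of discontinuation criteria, but Section 3.5 contains no ALT threshold.

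**5. The halt count.** More than two means at least 3, out of 5 subjects. Each subject in the disputed band contributes 0 or 1, which is 1/3 of the trigger.

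As illustration only, let a be the per-patient chance of a liver stop outside the disputed band and b the chance of falling in it. The documents give neither, so all values are assumptions. The chance of a halt is P(X ≥ 3), with X ~ Binomial(5, a) if the band continues and Binomial(5, a + b) if it stops.

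| a | b | Band continues | Band stops |
|---|---|---|---|
| 0.05 | 0.05 | 0.0012 | 0.0086 |
| 0.05 | 0.10 | 0.0012 | 0.0266 |
| 0.05 | 0.20 | 0.0012 | 0.1035 |
| 0.10 | 0.10 | 0.0086 | 0.0579 |
| 0.10 | 0.20 | 0.0086 | 0.1631 |

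For example, with a = 0.10 and b = 0.10, P(X ≥ 3) at p = 0.20 is 10(0.2³)(0.8²) + 5(0.2⁴)(0.8) + 0.2⁵ = 0.0512 + 0.0064 + 0.00032 = 0.0579. The finding does not depend on these figures.

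**The case against.** The best reply is that the text already ranks the two rules. The stopping wording is mandatory, the monitoring wording is permissive, and the return clause puts the stopping criteria first. On that reading a careful user arrives at one action, and the fault is an unusable provision rather than opposite instructions. This has some force, but it does not dispose of the point. Item 6, the first increased-monitoring criterion and the step-down bullet all presuppose that some subjects in the 5 to <8xULN band stay on treatment. No reading leaves all of the text in operation, and staff could reasonably act on the printed permission.

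Second, both routes require contact with the drug company within 24 hours, so a conflict would probably be noticed. That lowers the risk. It does not supply a rule for the band.

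Third, the halt link is secondary. Section 3.6 counts actual discontinuations, so the count itself is clear once each decision is made; the ambiguity lies in who is discontinued. The consequence is a pause in enrollment and a review, not automatic termination. By the time three subjects have been discontinued, at most 5 − 3 = 2 remain to be enrolled. These limits stand. The case for correction rests mainly on the patient-level safety rule.

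**Conclusion.** The concern holds. Section 5.1.2 gives two incompatible actions for a subject with ALT ≥5x and <8xULN, bilirubin <2xULN, no symptoms attributed to liver injury or hypersensitivity, and weekly monitoring available. This follows from the text alone. The thresholds in item 2, item 6 and the monitoring criteria are legible, so it does not turn on a lost symbol. Each such subject moves the Section 3.6 count by 0 or 1 against a trigger of 3 of 5, depending on the reading. How often it would happen cannot be estimated from the documents. Because the conflict sits in a mandatory safety rule, it must be corrected even if cases prove rare.

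**What to change.** Reconcile stopping items 2 and 6, the continuation sentence that follows the stopping list, and the increased-monitoring criteria with their step-down bullet, so that each combination of ALT band, bilirubin, symptoms and ability to monitor has exactly one action. A single table would do this most safely. Check item 5 at the same time: it stops any ALT ≥3xULN that cannot be followed weekly for 4 weeks, whereas the 5 to <8x monitoring criterion asks for only 2 weeks. A subject who can be followed for 2 weeks but not 4 would still face both instructions if item 2 alone were changed.

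Then have Section 3.6, criterion 1, cite the reconciled rule by section number, so that a countable liver discontinuation has one definition. Which threshold and action apply is for the sponsor and medical monitor to decide; this review takes no position.

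The cost is a wording amendment to Section 5.1.2 and a cross-reference in Section 3.6, with no added procedures.
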